14.2 Data Analysis

14.2.1 Analysis Population

Primary analysis will be conducted on all outcome data obtained from all participants as randomised and regardless of protocol adherence, i.e. intention to treat (ITT) analysis. Per-protocol analysis will also be conducted which will involve a comparison of treatment groups that includes only those participants who completed the treatment originally allocated. In view of the risk of bias arising from either analysis alone in a non-inferiority trial, we will conclude that non-inferiority of the intervention has been proven only if it is demonstrated in both analyses.

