8 TRIAL INTERVENTIONS

8.1 Study Intervention and Comparator (standard care)

When a febrile infant (under three months of age) attends hospital they should undergo blood and urine testing and may receive broad-spectrum parenteral antibiotics in the EDs or assessment unit pending laboratory results. This initial hospital assessment will be unaffected by the EASY study.

Clinicians will be free to perform investigations and administer parenteral antibiotics (standard care) during that initial assessment without delay.

Administration of initial parenteral antibiotics, if required based on national clinical guidelines and local policy, should not be delayed pending consent discussions.

Screening should occur once initial laboratory results are known and only eligible “low risk” infants will be invited to participate in the trial.

Randomisation must occur within 24 hours of hospital attendance.

Eligible “low risk” participants will be randomised in a 1:1 ratio to one of two treatment groups.

Intervention: Oral antibiotics and continuation of oral treatment at least until urine culture results are known (typically after 36 to 48 hours).

Comparator: Continuation of parenteral antibiotics (standard care) at least until urine culture results are known (typically after 36 to 48 hours).

Section 9 of the protocol, outlines the oral and parenteral antibiotics to be used in the EASY study.

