9.7 Study Drug Termination Criteria

Antibiotic treatment may be ended or switched based on clinical assessment during admission or at dedicated telephone reviews. The study drug may also be terminated once urine culture results are known and if no longer clinically indicated.

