10.1 Primary Outcome

The primary outcome is treatment failure (i.e. additional parenteral antibiotics) within seven days of randomisation.

Additional parenteral antibiotics in the standard care group is defined as:

- (i) administration of an additional parenteral antibiotic not prescribed as part of initial empirical treatment
- (ii) a change of parenteral antibiotics from standard empirical treatment
- (iii) re-commencing parenteral antibiotics after the decision to terminate parenteral antibiotics.

For the intervention group additional parenteral antibiotics are defined as administering parenteral antibiotics for any reason.

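### The per-protocol set can drop oral-arm failures selectively, so the required second non-inferiority test leans towards passing and adds little beyond ITT

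*Protocol*

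**What the plan says.** Protocol section 14.2.1 makes the primary analysis cover "all participants as randomised and regardless of protocol adherence, i.e. intention to treat (ITT) analysis". The per-protocol comparison "includes only those participants who completed the treatment originally allocated". Because either analysis alone may be biased in a non-inferiority trial, the section adds that "we will conclude that non-inferiority of the intervention has been proven only if it is demonstrated in both analyses".

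Section 10.1 sets the endpoint: "The primary outcome is treatment failure (i.e. additional parenteral antibiotics) within seven days of randomisation". The arms then have different definitions. "For the intervention group additional parenteral antibiotics are defined as administering parenteral antibiotics for any reason". In the standard care group, failure means an added parenteral agent, a changed one, or "re-commencing parenteral antibiotics after the decision to terminate parenteral antibiotics".

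Section 8.1 describes the allocated intervention as "Oral antibiotics and continuation of oral treatment at least until urine culture results are known (typically after 36 to 48 hours"). The comparator is parenteral treatment continued over the same period. Section 9.7 permits departures: "Antibiotic treatment may be ended or switched based on clinical assessment during admission or at dedicated telephone reviews".

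The protocol does not say what completing treatment means for the per-protocol set. The adherence allowance in section 10.2 (no more than two missed doses) is a secondary outcome and is not linked to that set.

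**The concern.** Membership of the per-protocol set depends on something that happens after randomisation and, in the oral arm, overlaps with the primary outcome. An oral-arm infant given parenteral antibiotics before the culture result meets the section 10.1 definition of failure and has also stopped short of the allocated treatment in section 8.1. The endpoint itself triggers the exclusion.

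The comparator arm behaves differently. Its allocation is a route. Adding or changing a parenteral agent leaves the infant on that route, and restarting after a decision to stop can follow a completed course. Most comparator failures can therefore stay.

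The dual requirement is there so that one analysis guards against bias in the other. If the second analysis sheds failures mainly from the oral arm, it loses that role, and readers would still be told that both analyses agreed.

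**Working it through.** **Inputs.** Section 14.1: failure rate 0.5% (taken as equal in both arms), margin 2%, 90% power, one-sided 97.5% confidence interval, 524 evaluable, 10% loss, 584 randomised. Section 8.1: 1:1 allocation. Section 14.2.2: non-inferiority if the upper bound for the risk difference is below 2%. Assumed: the share f of oral failures dropped from the per-protocol set, varied from 0 to 1.

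**Step 1: the plan's own figure.**
n per arm = (1.960 + 1.282)² × 2 × 0.005 × 0.995 / 0.02² = 10.51 × 0.00995 / 0.0004 ≈ 261.4, so 262 per arm and 524 in total. 524 / 0.90 = 582.2, so 583, or 584 as 292 per arm. The stated size reproduces.

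**Step 2: what the test tolerates at 262 per arm.**
Wald upper bound: p₁ − p₀ + 1.96 √[p₁(1−p₁)/n₁ + p₀(1−p₀)/n₀]. Newcombe upper bound: p₁ − p₀ + √[(u₁ − p₁)² + (p₀ − l₀)²], with Wilson limits u₁ and l₀.

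| Oral v control failures | Wald | Newcombe |
|---|---|---|
| 0 v 0 | 0.00% | 1.45% |
| 0 v 1 | 0.36% | 1.10% |
| 1 v 1 | 1.06% | 1.78% |
| 2 v 1 | 1.67% | 2.38% |
| 3 v 1 | 2.25% | 2.95% |

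The result turns on one or two oral failures, so losing a few from the set matters.

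**Step 3: chance that the per-protocol test passes when oral is worse by the full margin.**
True rates are 2.5% oral and 0.5% control. Expected failures are 262 × 0.025 = 6.55 and 262 × 0.005 = 1.31. Let a and b be the oral and control failures and k the oral failures dropped, with a ~ Bin(262, 0.025), b ~ Bin(262, 0.005) and k ~ Bin(a, f). The pass probability is the sum, over all a, b and k, of the probability of each outcome in which the upper bound for (a−k)/(262−k) v b/262 is below 2%. No control failures and no event-free infants are dropped.

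| Share f dropped | Mean oral failures kept, 6.55(1−f) | Pass, Wald | Pass, Newcombe |
|---|---|---|---|
| 0 | 6.55 | 5.1% | 1.5% |
| 0.25 | 4.91 | 15.3% | 5.0% |
| 0.50 | 3.28 | 39.7% | 16.0% |
| 0.75 | 1.64 | 79.5% | 46.6% |
| 1 | 0 | 100% | 100% |

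The f = 0 row is the ITT result. Its departure from 2.5% reflects how each interval behaves with few events and has nothing to do with the per-protocol rule.

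**Step 4: the joint rule.**
At every f in this model, the probability that both tests pass equals that of ITT alone: 5.1% (Wald) or 1.5% (Newcombe). Dropping oral failures lowers the per-protocol bound, so the second test never blocks a claim that ITT allows.

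**The case against.** A reader might infer that the rule removes every oral failure by definition, so that the per-protocol test cannot fail whatever the true rate. The documents do not support that. Allocated oral treatment need last only until the culture result, typically 36 to 48 hours, while failure is counted to day 7. An infant who reaches the culture result and then receives parenteral antibiotics can stay in the set as a failure. Suppose 13 oral and 1 control failures, with 10 of the 13 dropped. Then 3/252 v 1/262 gives an upper bound of 2.34% (Wald) or 3.08% (Newcombe), and the test correctly fails. Certain passing needs the strictest reading, in which any parenteral antibiotic to day 7 means non-completion, and the protocol does not state that reading.

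A reader might also infer an inflated risk of a false claim. That does not follow either: ITT counts every event and must also pass.

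Two further points have some force. The completion rule applies to both arms, and it is not stated whether a comparator infant with a changed agent has completed. Some control failures could therefore leave too, which would push the other way, although only about 1.3 are expected. It is also true that details of analysis sets often belong in the SAP. Here, however, the protocol states the completion rule itself and makes the resulting set decisive, so this is a stated rule to correct and not an omission.

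**Conclusion.** The point stands as a bias in the second test. On-treatment oral failures leave the per-protocol set because they are failures, while most control failures can remain, so the test leans towards passing and protects little beyond ITT. At a true difference equal to the margin, its chance of passing rises from 5.1% (Wald) or 1.5% (Newcombe) with no oral failures dropped to 39.7% or 16.0% with half dropped.

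These figures rest on 262 per arm, a control rate of 0.5%, no control failures dropped, and assumed values of f. Where f lies depends on how many failures come before the culture result and on how completion is read, and the protocol settles neither. The overall conclusion is no more prone to a false claim than ITT alone. What is lost is the corroboration that section 14.2.1 promises.

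**What to change.** Amend section 14.2.1, and carry the same text into the SAP before the final analysis:

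- Define the per-protocol set identically in both arms: eligible infants who received the allocated route from the first post-randomisation dose up to the culture result or the failure event, whichever comes first.
- State that, once the allocated route has been started, no infant is excluded because of an event meeting section 10.1, and that such infants count as failures.
- Give one explicit rule, applied equally to both arms, for infants who never started the allocated route, and report their number and outcomes by arm. This needs its own rule because an oral-arm infant kept on parenteral treatment from the outset also meets section 10.1, so excluding such infants without comment would bring the problem back.

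The cost is a few sentences. No new data are needed, since Table 6 already schedules collection of post-randomisation antibiotic administration and urine culture results, and clinical management does not change. The downside is that the per-protocol result may be less favourable to oral treatment.

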14.2.2 Statistical Methods

Baseline characteristics, follow-up measurements and safety data will be described using appropriate descriptive summary measures depending on the scale of measurement and distribution.

Analyses for the primary outcome will be 1-sided and at a significance level of 0.025 and investigated using generalised linear models (GLM) to estimate the risk difference (RD). The difference in treatment failure rate (95% CI) will be compared to the non-inferiority margin of 2%. Non-inferiority is established by showing that the upper bound of a one-sided 97.5% confidence interval for the difference in treatment failure rate is <2%.

A secondary comparison of the primary outcome between the two groups will be investigated using GLM, adjusting for site, sex, age, antibiotic use and other covariates

All remaining analyses for secondary outcomes will be two-sided and at a significance level of 0.05.

Binary outcomes between the two groups will be investigated using GLM, adjusting for covariates.

Comparison of continuous outcomes between the two groups will be investigated using independent t-tests or ANCOVA if appropriate or nonparametric equivalents.

We will include sensitivity analyses looking at treatment failure (day 28) and escalation in care (day 7 and day 28) for those children with a confirmed UTI*.

Statistical diagnostic methods will be used to check for violations of the assumptions, and transformations will be performed where required.

A detailed statistical analysis plan (SAP) will be written by the trial statistician prior to the final analysis.

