8.2 Assignment of Intervention

8.2.1 Sequence Generation

Participants will be randomised using an automated web-based or telephone system via randomly permuted blocks in a 1:1 ratio. There will be stratification by recruitment site, sex, age (29-60 days/61-90 days) and antibiotic use.

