14 STATISTICAL CONSIDERATIONS

14.1 Sample Size

With a treatment failure rate (i.e. additional parenteral antibiotics within 7 days of randomisation) of 0.5% and a non-inferiority margin of 2%, 524 participants are required based on 90% power and a 1-sided 97.5% Confidence Interval. Of the required population, it is estimated that up to 10% might not provide 7-day follow up. Therefore, a sample size of 584 is needed to obtain the 524 required for analysis.

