14.4 Additional Analysis

Exploratory analyses for the primary outcome will be reported using interaction tests (treatment group by subgroup) and 99% confidence intervals for the following subgroups:

- I. Age (29-60 days, 61-90 days)
- II. Site
- III. Sex
- IV. Antibiotics pre randomisation
- V. Confirmed UTI*

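### The primary non-inferiority verdict rests on a GLM risk difference with no interval method named; with about 2.6 events expected, the usual Wald bound would give about 5% false non-inferiority instead of 2.5%

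*Protocol*

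**What the plan says.** Protocol section 14.1 sizes the trial as follows: "With a treatment failure rate (i.e. additional parenteral antibiotics within 7 days of randomisation) of 0.5" per cent and "a non-inferiority margin of 2%, 524 participants are required", "based on 90% power and a 1-sided 97.5% Confidence Interval". Section 8.2.1 allocates "via randomly permuted blocks in a 1:1 ratio", so 524 evaluable infants means 262 per arm.

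Section 14.2.2 says that the primary outcome is "investigated using generalised linear models (GLM) to estimate the risk difference (RD"), and then: "The difference in treatment failure rate (95% CI) will be compared to the non-inferiority margin of 2" per cent. Success requires the upper one-sided 97.5% bound to lie below 2%, and section 14.2.1 requires this in both the ITT and the per-protocol analysis. No link function, interval construction or sparse-event rule is given. The section offers general diagnostics and transformations, and a SAP to be written before the final analysis.

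A secondary comparison of the same outcome is "investigated using GLM, adjusting for site, sex, age, antibiotic use and other covariates". Section 14.4 adds: "Exploratory analyses for the primary outcome will be reported using interaction tests (treatment group by subgroup) and 99% confidence intervals". Site is one of the listed subgroups, and section 7.1 plans at least 18 sites.

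**The concern.** A GLM risk difference is a sound estimator, but its bound can be obtained in several ways. These ways agree when events are plentiful and diverge when there are two or three. The most common software output is the estimate plus 1.96 standard errors (Wald). With rare events that bound sits too low, because its standard error is computed from observed proportions near zero. With no events the standard error is zero.

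A false claim of non-inferiority would support oral treatment in infants aged 29 to 90 days on weaker evidence than the stated 2.5% error implies. The timing also matters. The SAP is due only before the final analysis, its author is the trial statistician, and section 8.2.4 says that the trial statistician is unblinded. The interval could therefore be chosen when events by arm are known.

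**Working it through.** **Inputs.** Failure rate 0.5%, margin 2%, one-sided alpha 0.025, 90% power, 524 evaluable and 584 randomised (section 14.1); 1:1 allocation (section 8.2.1), so 262 or 292 per arm.

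**1. The plan's own figure.** Unpooled normal approximation:

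n per arm = (1.960 + 1.282)² × 2 × 0.005 × 0.995 / 0.02² = 261.4, so 262 per arm and 524 in total. Then 524 / 0.90 = 582.2, or 584 after rounding up to a size that gives equal arms with slight slack. The 524 is reproduced with the variance form that a Wald interval uses.

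**2. Expected events.** 262 × 0.005 = 1.31 per arm, 2.62 in total. At the null (2.5% v 0.5%) the oral arm expects 262 × 0.025 = 6.55. With 0.5% in both arms, P(no events in a given arm) = 0.995^262 = 0.269. P(at least one arm without events) = 1 − (1 − 0.269)² = 47%, and P(no events at all) = 0.995^524 = 7.2%.

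**3. Upper bounds for particular results, 262 per arm.** Wald: p1 − p0 + 1.96 × √[p1(1 − p1)/262 + p0(1 − p0)/262]. For 2 v 0: 0.763% + 1.96 × 0.538% = 1.82%. A fitted identity-link binomial GLM gives the same value. The score and profile-likelihood bounds invert the corresponding tests, with the rates re-estimated under each candidate difference.

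| Events, oral v parenteral | Wald | Profile likelihood | Score (Miettinen-Nurminen) |
|---|---|---|---|
| 0 v 0 | 0.00% | 0.73% | 1.45% |
| 2 v 0 | 1.82% | 2.34% | 2.74% |
| 2 v 1 | 1.67% | above 2% | 2.40% |

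At 2 v 0 and 2 v 1, Wald declares non-inferiority and the other two do not.

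**4. False non-inferiority.** Sum the product of the two binomial probabilities over all results whose bound is below 2%, with the true oral rate set to the control rate plus 2%. At 262 per arm:

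| Control rate | Wald | Profile likelihood | Score |
|---|---|---|---|
| 0% | 10.4% | 3.2% | 0.5% |
| 0.25% | 6.8% | 2.5% | 1.2% |
| 0.5% (protocol) | 5.05% | 2.5% | 1.5% |
| 0.88% (1/114, section 4.2 cohort) | 4.0% | 2.8% | 1.9% |
| 1% | 3.9% | 2.9% | 2.0% |
| 2% | 3.4% | 2.9% | 2.2% |

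At a 3% control rate, Wald is 3.0% and score 2.3%. With all 584 analysed (292 per arm), Wald is 4.6% at 0.5% and 6.8% at 0%.

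**5. Probability of declaring non-inferiority at 0.5% in both arms, 262 per arm.** Wald 87.0%, profile likelihood 71.5%, score 56.6%. Wald disagrees with profile likelihood in 87.0 − 71.5 = 15.5% of trials and with score in 87.0 − 56.6 = 30.4%. In every such trial Wald is the one that declares non-inferiority.

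**6. Adjusted and interaction models.** With 2.62 expected events over at least 18 sites, the mean is 2.62 / 18 = 0.15 events per site. Three events can fall in at most three sites, leaving 15 or more with none.

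**The case against.** The strongest reply is that the protocol never says Wald. A profile-likelihood bound fits the quoted text, holds 2.5-3.2% and does not collapse at 0 v 0. Interval construction is also ordinary SAP content, and the SAP is not at hand. This stands: a reader might infer that the protocol commits to an invalid bound or that a GLM risk difference is itself wrong, and the documents support neither. Reproducing the 524 shows how the trial was sized, not how it will be analysed.

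A reader might also infer a general error of 5-10%. That holds only for control rates between 0.5% and zero; the protocol's own input gives about 5%, and higher rates give 3-4%. The 1.3 events per arm describe the design alternative, not the null at which the error is computed. Requiring success in both populations can only lower the joint error. How far depends on the overlap of the two populations, which the documents do not give. The 30% disagreement is measured against a conservative comparator; against profile likelihood it is about 15%.

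Finally, the adjusted model is secondary and the site interaction exploratory, so neither decides the trial. It would be too strong to say that they cannot be fitted, since site could enter as a random effect. With about three events, however, they could not be informative.

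What remains is more than a missing detail. Whether the stated 2.5% holds depends on an unnamed choice, and the stated sample size reaches close to its stated power only under the choice that breaks it.

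**Conclusion.** The concern holds conditionally. If the Wald bound is used, the one-sided error at the protocol's own inputs is about twice the stated level: 5.05% with 524 analysed and 4.6% with 584. Two standard alternatives, one of them from the planned GLM, avoid the failure. Profile likelihood stays close to nominal, slightly above it at some control rates, and score stays below it. The interval choice alone changes the verdict in roughly 15% to 30% of trials run at the design rate, so it should not be left open until arm-level events may be known.

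The figures assume independent binomial outcomes, equal arms and a single unadjusted analysis.

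**What to change.** - **Primary analysis.** Before anyone sees events by arm, name a bound that is valid with sparse data for the unadjusted risk difference, in both the ITT and per-protocol analyses: the Miettinen-Nurminen score bound, or profile likelihood from the planned binomial GLM. Both give a usable result at 0 v 0.
- **Secondary adjusted comparison.** Replace the model with site and further covariates by a Mantel-Haenszel or stratified score risk difference over age group and pre-randomisation antibiotics only. The stratified score form is the safer of the two, because the usual Mantel-Haenszel variance is also zero when there are no events.
- **Exploratory analysis.** Replace the site interaction for the primary outcome with a listing of events by site and arm.
- **Power.** Restate it for the chosen bound. At 524 evaluable and 0.5% in both arms it is about 57% (score) or 72% (profile likelihood), against the stated 90%; even Wald gives 87%. With score, 90% needs about 448 per arm, which is 896 evaluable and about 896 / 0.90 = 996 randomised.

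The wording costs little and the methods are in standard software. The real cost is acknowledging the lower power.

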4.2 Rationale for the Study

In the UK, the diagnosis and management of febrile young infants is primarily guided by the National Institute for Health and Care Excellence (NICE). Clinical guidelines CG54, NG143 and NG111 recommend that all febrile infants, 90 days and younger, with a suspected UTI are admitted to hospital and treated with parenteral antibiotics [13-15]. However, this guidance is not always followed. In preparation for this project, we conducted the Febrile Infants Diagnostic assessment and Outcome study (FIDO) study [1] as an observational cohort study in six Paediatric Emergency Research in the UK and Ireland (PERUKI) sites between 31 August 2018 and 01 September 2019 [1]. The aims were to report the aetiology of infections amongst young febrile infants, validate clinical practice guidelines and assess current UK practices. That pilot work demonstrated that the average Paediatric Emergency Department in the UK and Ireland sees approximately one infant per day with a history of fever (based on 1942 cases). Of those with fever on arrival to hospital (n=555), 500 (90%) were admitted to hospital and 423 (76%) received parenteral antibiotics [1]. However, of these 555 infants febrile on arrival to hospital, only 11 (2%) had bacterial meningitis or bacterial sepsis and (67) 12% had a UTI [1].

Of the 555 febrile infants in the study, 114 (21%) met the American Academy of Paediatrics definition of “low risk” [>28 days of age, appear well, CRP of <20mg/l, absolute neutrophil count (ANC) < 5,200/mm³] and had abnormal urinalysis [2]. According to NICE guidance, all these infants should have been admitted to hospital and been given parenteral antibiotics [13-15] but only 81 (71% of the 114) were admitted to hospital and 33 (29%) were discharged home from ED with no oral antibiotic therapy. Amongst these 114 lower risk infants, 4 (4%) were diagnosed with a confirmed UTI and there were no cases of meningitis or bacterial sepsis. There was one case of treatment failure occurring in an infant who was not given parenteral antibiotics.

This pilot work demonstrates that clinicians do not routinely follow NICE guidance and that there appears to be considerable uncertainty regarding the management of well appearing febrile infants with abnormal urinalysis.

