7.3.1 Inclusion Criteria

1. 29 to 90 days of age (Infants from their 29th day of life to their 90th day of life inclusive. Day of birth is day 1 of life)
2. Suspected urinary tract infection (UTI) requiring treatment with antibiotics
3. History of fever as defined as temperature $\geq 38^{\circ}\text{C}$ measured by any method OR likely fever in last 24 hours including subjective fever reported by caregiver

4. Abnormal urinalysis defined as: (1) abnormal urinary dipstick test (leucocyte esterase $\geq 1+$, or nitrite \geq Trace) OR (2) abnormal urine microscopy (≥ 5 white cells per high-power field in centrifuged urine or ≥ 10 white cells per mm³ in un-centrifuged urine or bacteriuria with any bacteria per high power field)
5. Well on global clinical assessment using the paediatric assessment triangle* assessed by a consultant grade doctor. [28]

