10.2 Secondary Outcomes

1. Treatment failure (i.e. additional parenteral antibiotics) assessed at day 28
2. Escalation in care defined as, escalation in the level of care (i.e. admission from home, admission to intensive care or a high dependency unit) OR change in antibiotic therapy OR death due to poor response. Assessed at 7 and 28 days.
3. Time to defervescence
4. Time to normal feeding (as reported by parent/guardian)
5. Time to normal activity (as reported by parent/guardian)
6. Length of stay
7. Antibiotic-associated adverse events (including diarrhoea and allergic reaction)
8. Antibiotic adherence (full course taken or no more than two missed doses)
9. Paediatric quality of life (measured using PedsQL acute infant version) within 24 hours of randomisation, day 7 and day 28
10. Family impact (measured using PedsQL Family Impact Module acute version) at day 7
11. Health service use and costs

11 SCREENING, CONSENT and RECRUITMENT

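### The only rule stated for non-binary secondary outcomes leaves stratum adjustment optional and cannot handle censoring in the three recovery times

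*Protocol*

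**What the plan says.** All references are to the protocol.

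- **Outcomes.** Section 10.2 lists "Time to defervescence", with no time origin or event definition, and parent-reported times to normal feeding and to normal activity. Length of stay and PedsQL scores are on the same list.
- **Methods.** Section 14.2.2 recognises two classes. One is covered by "Binary outcomes between the two groups will be investigated using GLM, adjusting for covariates", the other by "Comparison of continuous outcomes between the two groups will be investigated using independent t-tests or ANCOVA if appropriate or nonparametric equivalents". It adds assumption checks, transformations where needed, and a SAP to be written before the final analysis. It names no time-to-event method and no censoring rule.
- **Randomisation.** Section 8.2.1: "There will be stratification by recruitment site, sex, age (29-60 days/61-90 days) and antibiotic use". These four factors are named as covariates only for the secondary comparison of the primary outcome.
- **Follow-up.** Table 6 records symptoms within 24 hours, at 36–48 hours, at day 7 (±1) and at day 28 (±3). Section 14.1 expects up to 10% without 7-day follow-up. Section 14.5 allows multiple imputation or Bayesian methods if missing data make them necessary.
- **Fever at entry.** Besides a measured temperature, Section 7.3.1 accepts "OR likely fever in last 24 hours including subjective fever reported by caregiver". Section 8.1 allows randomisation up to 24 hours after attendance.

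**The concern.** There are two separate weaknesses in one sentence.

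First, the design stratifies on four factors, but the rule for continuous outcomes puts an unadjusted t-test first and leaves ANCOVA to judgement, with no covariates named. Binary outcomes are to be adjusted. The gap matters most for length of stay, because Section 12.1 leaves discharge to the local clinical team and site is therefore likely to explain much of the variation.

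Second, three outcomes are times to an event, and no stated method is built for them. A t-test, ANCOVA or standard rank test needs an observed value for every infant. An infant still febrile or feeding poorly at last contact, or lost before recovery, has none. For a discharged infant who recovers between about 48 hours and day 7, the time rests on parental recall or is known only to within days.

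The recovery times carry weight in this trial. At the planned 0.5% failure rate, 262 analysed infants per arm give about 262 × 0.005 = 1.3 primary events per arm, so much of the evidence on clinical response comes from the secondary outcomes.

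**Working it through.** **1. The plan's own figure.** Inputs from Section 14.1: failure rate p = 0.005 in both arms, margin 0.02, one-sided 0.025, power 90%.

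n per arm = (1.960 + 1.282)² × 2p(1 − p) / 0.02² = 10.51 × 0.00995 / 0.0004 = 261.4, so 262 per arm and 524 in total. Allowing for 10% loss, 262 / 0.9 = 291.1, so 292 per arm and 584 in total. Both figures reproduce. The protocol gives no sample size for the three times, and nothing below alters 524 or 584.

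**2. Which rule reaches which outcome.** Escalation in care, adherence and treatment failure at day 28 are binary. Length of stay and PedsQL scores are continuous. The three times are not binary, so the continuous sentence is the only stated rule left for them. This is an inference by elimination; the text does not make the assignment.

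**3. Effect of dropping unresolved infants.** Assume, for illustration only, exponential time to defervescence with mean 36 h, and that a share s of infants still febrile at 48 h is lost and dropped.

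- P(time > 48 h) = exp(−48/36) = 0.2636
- Contribution of those infants to the mean = 0.2636 × (48 + 36) = 22.14 h
- Mean among those kept = (36 − 22.14s) / (1 − 0.2636s)

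| s | Dropped overall | Mean among those kept |
|---|---|---|
| 10% | 2.6% | 34.7 h |
| 25% | 6.6% | 32.6 h |
| 50% | 13.2% | 28.7 h |

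A simulation of one million times agreed to within 0.1 h. If s were 10% in one arm and 25% in the other, with no true difference, the apparent difference would be 34.7 − 32.6 = 2.1 h. If loss is random and equal, the test stays valid: simulated t-tests (292 per arm, 10% random loss, 2,000 runs per scenario) rejected a true null in 4.3% to 5.6% of runs.

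**4. Infants afebrile at entry (defervescence only).** Section 4.2 reports 555 infants febrile on arrival and 1942 cases with a history of fever. Reading the first as a subset of the second, 555 / 1942 = 28.6%. That cohort was not restricted to abnormal urinalysis, so the trial's share is unknown and a range is shown. The detectable hazard ratio is exp[(1.960 + 0.842) / √(events/4)] at two-sided 0.05 and 80% power, taking 524 analysed infants and assuming every fever resolves.

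| Febrile share | Events | Detectable hazard ratio | Power at ratio 1.3, time-to-event in febrile infants | Power at ratio 1.3, t-test with afebrile infants scored zero |
|---|---|---|---|---|
| 28.6% | 150 | 1.58 | 36% | 22% |
| 50% | 262 | 1.41 | 56% | 40% |
| 75% | 393 | 1.33 | 74% | not run |
| 100% | 524 | 1.28 | 85% | 85% |

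Under zero scoring, the mean difference shrinks in proportion to the febrile share. At a rate ratio of 1.3 the full difference is 36 − 36/1.3 = 8.3 h, and at 28.6% febrile it is 0.286 × 8.3 = 2.4 h. If afebrile infants are instead left out as having no defined time, this dilution does not arise. The protocol states neither rule.

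**5. Strata.** Adjustment multiplies the residual variance by about 1 − R², where R² is the share of variation explained by the strata. The documents give no R² for length of stay or PedsQL, so the gain is not quantified here.

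**The case against.** The strongest reply is that a SAP is announced, that it commonly settles these matters, and that a survival analysis there would contradict nothing in the protocol. That is fair for event definitions and time origins. It does not fully answer the point, because Section 14.2.2 does commit to methods, and the one it commits to for non-binary outcomes is weaker than an equally cheap alternative. Section 8.2.4 also has the trial statistician unblinded, so a choice left at "if appropriate" level is better closed early.

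Several stronger readings are tempting, and the documents do not support them:

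- *The three times will be t-tested.* The text never assigns them; it only leaves no other rule.
- *The strata are ignored.* ANCOVA is allowed and could include them. Adjustment is optional, not excluded.
- *Unresolved or lost infants are dropped.* No section says so, Section 14.5 permits imputation, and Section 12.1 follows infants to day 28 even after antibiotics stop. The 10% is a ceiling on missing 7-day follow-up, not a count of unresolved infants.
- *About 71% have no fever to resolve, so any difference shrinks to 0.29 of its size.* The figure comes from a broader cohort. Being afebrile on arrival does not rule out later fever, and Section 9.9 permits antipyretics. The shrinkage also needs zero scoring. It does not concern feeding or activity.
- *Time to defervescence should be restricted to measured fever.* At the cohort's share this would leave about 524 × 0.286 = 150 infants and exclude those with reported fever whom the trial chose to enrol. Table 6 lists symptoms and physical examination, but does not show that serial temperatures are captured.

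**Conclusion.** The concern holds in a limited form. Section 14.2.2 makes stratum adjustment optional for continuous outcomes in a trial stratified on four factors. It states no method that can deal with censoring in the three recovery times.

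The size depends on facts the protocol does not give. With equal random loss the error rate is sound. With selective loss of slow recoverers, the illustrative mean falls by about 1 to 7 h for 10% to 50% loss after 48 h, and the comparison is biased only if that loss differs between arms. The protocol offers no evidence that it will. For defervescence, power at a rate ratio of 1.3 could lie anywhere from 22% to 85%, according to the febrile share (29% to 100%), if afebrile infants are scored zero. These figures rest on an assumed exponential time with a 36 h mean.

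Only secondary outcomes are affected. The change is worth making because it costs almost nothing.

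**What to change.** In Section 14.2.2 and the SAP:

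1. **Length of stay and PedsQL.** Replace the unadjusted t-test as the stated method with a regression (ANCOVA or a mixed model) adjusted for age group, sex, prior antibiotic use and site.
2. **The three recovery times.** Classify them as time-to-event outcomes measured from randomisation. Use Kaplan–Meier curves and a time-to-event model adjusted for the same factors, censored at last contact, and interval-censored if only contact times are known.
3. **Defervescence.** Keep all infants in the main analysis under a stated rule for those already afebrile at randomisation. Add a supportive analysis in infants with measured fever at baseline, if temperatures are recorded. Report the observed febrile share; until it is known, show planning figures over 29% to 100%.

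The cost is wording, slightly more analysis work, and a hazard ratio in place of a mean difference for the three times. The sample size does not change. Before relying on interval censoring or the supportive analysis, check what the CRF captures on recovery dates and temperatures.
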